3.11.5 Study Content

(1) In-hospital Management

1. Signing of Informed Consent

Each participant or their legal representative must provide informed consent before initiating any study-related procedures.

2. Physical Examination

Complete and document a physical examination, including heart rate, blood pressure, height, and weight.

3. Medical History

Complete a detailed medical history record, including age, gender, NYHA functional status, risk factors (hypertension, smoking, diabetes, etc.), and previous cardiovascular diseases (including myocardial infarction, percutaneous coronary intervention, etc.).

4. Laboratory Examinations

Including routine blood test + C-reactive protein (CRP), liver function, renal function, and routine lipid profile.

5. Electrocardiogram (ECG)

Record a 12-lead ECG at baseline. Document cardiovascular events such as severe arrhythmias occurring during hospitalization.

6. Echocardiography

Complete at least one echocardiographic examination within 3 days after MI.

(2) Post-discharge Follow-up (6th, 12th, 24th, and 60th months)

Laboratory Examinations

Including routine blood test + CRP, liver function, renal function, and routine lipid profile.

Safety and the patient's clinical status will be assessed at each follow-up time point after drug administration.

1. Medical History

Complete a detailed medical history record, supplementing any medical events occurring after enrollment in the trial (including symptoms, potential drug side effects, physical status, recurrence of MI/interventional events/hospitalization, death, etc.), as well as patient medication adherence.

2. Physical Examination

Complete and document a physical examination, including heart rate and blood pressure.

3. Electrocardiogram (ECG)

Routinely record a 12-lead ECG at 6th, 12th, and 24th months after MI.

4. Echocardiography

Complete an echocardiographic examination at 6th, 12th, 24th, and 60th months after MI.

3.11.6 Data Collection

| Items | Baseline (Before Discharge, ≤3 days) | Follow-up (3 months ±14 days) | Follow-up (6 months ±30 days) | Follow-up (12 months ±30 days) | Follow-up (24 months ±90 days) | Follow-up (60 months ±90 days) |
|--|---|-------------------------------------|-------------------------------------|---|---|---|
| Inclusion/ Exclusion Criteria | O | | | | | |
| Signing of Informed Consent | O | | | | | |
| Medical History Informatio n (Age, gender, height, weight, risk factors, clinical past | O | | | | | |

| | | | | | | |
|--|---|---|---|---|---|---|
| history, NYHA functional status, previous history of heart disease) | | | | | | |
| Medical History Information (Any medical events after enrollment in the trial) | | O | O | O | O | O |
| Medication History* | O | O | O | O | O | O |
| Physical Examination | O | Δ | Δ | Δ | Δ | Δ |
| Vital Signs | O | Δ | Δ | Δ | Δ | Δ |
| Coronary Angiography Images# | O | | | | | |
| Laboratory Examinations (Routine blood test + CRP, liver function, renal | O | | Δ | Δ | Δ | Δ |

| | | | | | | |
|--|---|---|---|---|---|---|
| function, routine lipid profile) | | | | | | |
| 12-lead ECG | O | | Δ | Δ | Δ | Δ |
| Echocardi ographic Results (LVEF%, LVIDd, LVIDs) and Original Images | O | | O | O | O | O |
| NYHA Functional Classificat ion | O | | | | O | O |
| KCCQ Score | | | | | O | O |
| MACE Events | | O | O | O | O | O |
| Drug Distributi on | O | O | O | O | O | |
| Drug- related Adverse Reactions | | O | O | O | O | |
| Medicatio n Adherenc e | | O | O | O | O | |

The timeline for data collection is shown in the table above:

Compulsory coronary angiography or laboratory blood tests during follow-up are prohibited. If a participant experiences an endpoint event, it is recommended to collect ECG and coronary angiography data.

*Medication-related information includes the patient's medication status before admission and after discharge.

O: Mandatory item.

Δ: Non-mandatory but recommended.

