3.3 Study Period

Recruitment period: 24 months. Follow-up time points: 6th, 12th, 24th, and 60th months after enrollment.

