3.7 Primary Endpoint

Incidence of major adverse cardiovascular and cerebrovascular events (MACCE) within 24 months after randomization, including all-cause death, recurrent myocardial infarction, stroke, hospitalization for heart failure, outpatient or emergency visits due to worsening heart failure, and repeat revascularization driven by angina pectoris.

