3.12 Statistical Methods

| Primary Endpoint | Statistical Methods | Analysis Time Point |
|--|---|--|
| Incidence of major adverse cardiovascular events (MACE, including cardiac death, non-fatal MI, non-fatal stroke, readmission for heart failure, etc.) within 24 months after randomization | Survival analysis, Kaplan-Meier survival curve, Log-rank test | 24th month after randomization |
| Secondary Endpoints | Statistical Methods | Analysis Time Point |
| All-cause death at 24 and 60 months after randomization | Survival analysis, Kaplan-Meier survival curve, Log-rank test | 24th and 60th months after randomization |
| Recurrent myocardial infarction at 24 and 60 months after randomization | Survival analysis, Kaplan-Meier survival curve, Log-rank test | 24th and 60th months after randomization |
| Stroke at 24 and 60 months after randomization | Survival analysis, Kaplan-Meier survival curve, Log-rank test | 24th and 60th months after randomization |
| Hospitalization for heart failure or outpatient/emergency visits due to worsening heart | Survival analysis, Kaplan-Meier survival curve, Log-rank test | 24th and 60th months after randomization |

| | | |
|--|---|--|
| failure at 24 and 60 months after randomization | | |
| Repeat revascularization driven by angina pectoris at 24 and 60 months after randomization | Survival analysis, Kaplan-Meier survival curve, Log-rank test | 24th and 60th months after randomization |
| Difference in left ventricular ejection fraction (LVEF%) measured by echocardiography compared to baseline after randomization | T-test, Wilcoxon rank-sum test | 24th month after randomization |
| Difference in left ventricular end-systolic diameter/body surface area% measured by echocardiography compared to baseline after randomization | T-test, Wilcoxon rank-sum test | 24th month after randomization |
| Difference in left ventricular end-diastolic diameter/body surface area% measured by echocardiography compared to baseline after randomization | T-test, Wilcoxon rank-sum test | 24th month after randomization |
| NYHA functional classification at 12 and 24 months after randomization | Wilcoxon rank-sum test, Chi-square test | 24th month after randomization |
| KCCQ score at 12 and 24 months after randomization | T-test, Wilcoxon rank-sum test | 24th month after randomization |
| Incidence of drug-related adverse events | Chi-square test | 1st, 3rd, 6th, 12th, and 24th months after randomization |

4. Sample Size Calculation

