This study adopts a 1:1 sample size ratio between the experimental group and the control group, with a one-sided α value set at 0.025 and a power (1- β) of 0.8. Based on preliminary study results and relevant clinical data (referring to PARADISE-MI, EMPACT-MI, COLCOT,

FLAVOUR series studies), event rate estimation will be performed using Kaplan-Meier survival analysis. Assuming an event rate of 16.5% in the control group and 13.2% in the experimental group, the expected enrollment period is 2 years. The sample size will be calculated using PASS software. Considering a 10% dropout rate, 1402 patients will need to be enrolled in each group, totaling 2804 patients.

5. Data Management and Confidentiality

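### The month-24 visit may fall 90 days early with no further contact planned before month 60, so some primary-endpoint events just before month 24 may not be ascertained for the 24-month analysis

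*Protocol*

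**What the plan says.** Protocol 3.7 defines the primary endpoint as "Incidence of major adverse cardiovascular and cerebrovascular events (MACCE) within 24 months after randomization". The table in 3.12 gives its analysis as "Survival analysis, Kaplan-Meier survival curve, Log-rank test", with month 24 as the analysis time point.

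The visit table in 3.11.6 has the columns "Follow-up (24 months ±90 days" and, next, "Follow-up (60 months ±90 days". MACE events are a mandatory item at both. Section 3.3 lists "Follow-up time points: 6th, 12th, 24th, and 60th months after enrollment", and 3.6 repeats these times and allows contact by telephone or in the clinic. The table adds a month-3 visit, but no section adds a contact between months 24 and 60.

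The protocol does not require event or vital status to be checked on or after the 24-month date when the visit takes place before it.

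**The concern.** The endpoint period and the visit that closes it do not match. A patient seen 90 days early has met the schedule with almost 3 months of the endpoint period still to run, and the next planned contact comes about 3 years later. A MACCE in that interval is not sought before the 24-month analysis.

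Two things are at stake. Events that count towards the primary endpoint may be missed. The last part of the 24-month curve also rests on fewer patients than it need do. An analysis plan can state how such patients are censored, but it cannot supply observations that the schedule does not collect. The point therefore belongs in the protocol's visit schedule.

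**Working it through.** **Inputs from the protocol.** Window of ±90 days (3.11.6); 24-month horizon (3.7); log-rank test (3.12). From Section 4: "Assuming an event rate of 16.5% in the control group and 13.2% in the experimental group", "one-sided α value set at 0.025", "power (1- β) of 0.8", a 2-year enrollment period, 10% dropout and 1402 patients per group.

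**Assumptions.** Section 4 gives no time point for the two rates; they are read here as 24-month risks. Hazards are exponential. The protocol says nothing about how visit dates will be distributed, so an even spread and the extreme are both shown.

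**Step 1: the plan's own figure.**
- Hazard ratio = ln(1 − 0.132) / ln(1 − 0.165) = 0.785, and its logarithm is −0.242.
- Events for 80% power (Schoenfeld) = 4 × (1.960 + 0.842)² / 0.242² ≈ 537.
- With uniform 2-year accrual and 4 years in total, patients are followed for 24 to 48 months. The average event risks are then 23.6% and 19.1%.
- 537 / (0.236 + 0.191) ≈ 1259 per group, and 1259 / 0.9 ≈ 1399. This is close to the stated 1402.
- If events count only to month 24, the same inputs give 537 / (0.165 + 0.132) / 0.9 ≈ 2009 per group. That gap is a separate and larger matter. It is needed here only because it sets the power from which the window's effect is measured.

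**Step 2: baseline with status known through 24 months.** Events = n × (0.165 + 0.132). Power = Φ(0.242 × √events / 2 − 1.960).
- After 10% dropout, n = 1262 per group: 375 events, power 0.65.
- Without dropout, n = 1402 per group: 416 events, power 0.69.

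**Step 3: how early is early.** 90 / 30.4375 = 2.96 months, and 24 − 2.96 = month 21.04. Up to 2.96 / 24 = 12% of the endpoint period can lie beyond an in-window visit.

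**Step 4: the bound, every visit at −90 days.** Risk at time t is 1 − (1 − p)^(t/24). At t = 21.04 the risks are 14.6% and 11.7%.

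**Step 5: visits spread evenly over ±90 days.** Half the patients are seen before month 24, on average 45 days early. Averaging the risk over the window, with follow-up capped at 24 months, gives 16.03% and 12.82%.

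| Case | Events, n = 1262 | Lost | Power | Events, n = 1402 | Lost | Power |
|---|---|---|---|---|---|---|
| Status known to month 24 | 375 | – | 0.65 | 416 | – | 0.69 |
| Even spread | 364 | 11 (2.9%) | 0.64 | 405 | 12 (2.9%) | 0.68 |
| All at −90 days | 332 | 43 (11.5%) | 0.60 | 369 | 48 (11.5%) | 0.64 |

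**Step 6: the risk set at month 24, even spread.** About half of 1262, or 631 per group, are followed to the full 24 months. Of these, 631 × 0.835 ≈ 527 (control) and 631 × 0.868 ≈ 548 (fexofenadine) are event-free and still at risk at that point. The end of the curve is thinner but far from empty.

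**The case against.** The strongest reply is that ±90 days is an attendance tolerance for a visit that also carries echocardiography, NYHA class and KCCQ, and that Kaplan-Meier and the log-rank test are built to handle unequal follow-up. The loss needs an assumed visit pattern: if visits cluster at the target date or run late, it is below 2.9%, and the 11.5% figure requires every patient to come exactly 90 days early. Gap events may also reach the case report form through adverse-event recording (7.1), and the month-60 visit asks again about events since enrollment. Censoring rules may properly sit in an analysis plan that is not shown.

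Most of this stands, and it makes the point small. It does not remove it. Censoring avoids miscounting but recovers no events, and it is unbiased only if early attendance is unrelated to risk. The event types listed in 3.9 are narrow, so adverse-event recording gives only partial cover. Recall at month 60 comes after the 24-month analysis.

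A reader might infer several stronger things that the protocol does not support:
- *Patients are closed out at month 21.* They remain in follow-up to month 60, and the month-24 visit is not described as an exit.
- *The 24-month estimate rests only on those seen on time or late.* Every patient contributes up to the censoring date; only the last increments use a reduced risk set.
- *The window takes power from 80% to about 75%.* An 80% baseline needs about 537 events, whereas 375 to 416 are expected by month 24.
- *The comparison is biased between groups.* The trial is double-blind with one schedule for both groups, and no mechanism is shown.
- *Early attenders will be counted as event-free to month 24.* No section says so, and 3.12 names time-to-event methods.

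**Conclusion.** The point holds as a minor one. The schedule as written can leave up to about 3 months of the primary-endpoint period unobserved at the time of the primary analysis, and no provision closes the gap.

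On the planning rates, the working estimate is a loss of about 2.9% of events and about 1 point of power. The bound is about 11.5% and about 5 points. Both rest on reading 16.5% and 13.2% as 24-month risks with exponential hazards; the working estimate also rests on an even spread of visit dates. The documents give neither the time point of the rates nor the distribution of visits. The case for acting is that the events can be had for almost nothing, not that the result is endangered.

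**What to change.** Amend the month-24 column in 3.11.6 in one of two ways:
- for event ascertainment, open the window at 24 months (0 to +90 days); or
- keep ±90 days for echocardiography, NYHA class and KCCQ, and require a telephone check of events and vital status on or after the 24-month date for anyone seen earlier. Section 3.6 already allows telephone follow-up.

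The limit on which events count needs no new wording, since 3.7 and 3.12 already set it at 24 months. The cost is a change to the schedule and either some telephone calls or a slightly later last visit before the primary analysis.

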3.12 Statistical Methods

| Primary Endpoint | Statistical Methods | Analysis Time Point |
|--|---|--|
| Incidence of major adverse cardiovascular events (MACE, including cardiac death, non-fatal MI, non-fatal stroke, readmission for heart failure, etc.) within 24 months after randomization | Survival analysis, Kaplan-Meier survival curve, Log-rank test | 24th month after randomization |
| Secondary Endpoints | Statistical Methods | Analysis Time Point |
| All-cause death at 24 and 60 months after randomization | Survival analysis, Kaplan-Meier survival curve, Log-rank test | 24th and 60th months after randomization |
| Recurrent myocardial infarction at 24 and 60 months after randomization | Survival analysis, Kaplan-Meier survival curve, Log-rank test | 24th and 60th months after randomization |
| Stroke at 24 and 60 months after randomization | Survival analysis, Kaplan-Meier survival curve, Log-rank test | 24th and 60th months after randomization |
| Hospitalization for heart failure or outpatient/emergency visits due to worsening heart | Survival analysis, Kaplan-Meier survival curve, Log-rank test | 24th and 60th months after randomization |

| | | |
|--|---|--|
| failure at 24 and 60 months after randomization | | |
| Repeat revascularization driven by angina pectoris at 24 and 60 months after randomization | Survival analysis, Kaplan-Meier survival curve, Log-rank test | 24th and 60th months after randomization |
| Difference in left ventricular ejection fraction (LVEF%) measured by echocardiography compared to baseline after randomization | T-test, Wilcoxon rank-sum test | 24th month after randomization |
| Difference in left ventricular end-systolic diameter/body surface area% measured by echocardiography compared to baseline after randomization | T-test, Wilcoxon rank-sum test | 24th month after randomization |
| Difference in left ventricular end-diastolic diameter/body surface area% measured by echocardiography compared to baseline after randomization | T-test, Wilcoxon rank-sum test | 24th month after randomization |
| NYHA functional classification at 12 and 24 months after randomization | Wilcoxon rank-sum test, Chi-square test | 24th month after randomization |
| KCCQ score at 12 and 24 months after randomization | T-test, Wilcoxon rank-sum test | 24th month after randomization |
| Incidence of drug-related adverse events | Chi-square test | 1st, 3rd, 6th, 12th, and 24th months after randomization |

4. Sample Size Calculation

This study adopts a 1:1 sample size ratio between the experimental group and the control group, with a one-sided α value set at 0.025 and a power (1- β) of 0.8. Based on preliminary study results and relevant clinical data (referring to PARADISE-MI, EMPACT-MI, COLCOT,

FLAVOUR series studies), event rate estimation will be performed using Kaplan-Meier survival analysis. Assuming an event rate of 16.5% in the control group and 13.2% in the experimental group, the expected enrollment period is 2 years. The sample size will be calculated using PASS software. Considering a 10% dropout rate, 1402 patients will need to be enrolled in each group, totaling 2804 patients.

5. Data Management and Confidentiality

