3.8 Secondary Endpoints

1. All-cause death at 24 and 60 months after randomization.
2. Recurrent myocardial infarction at 24 and 60 months after randomization.
3. Stroke at 24 and 60 months after randomization.
4. Hospitalization for heart failure or outpatient/emergency visits due to worsening heart failure at 24 and 60 months after randomization.
5. Repeat revascularization driven by angina pectoris at 24 and 60 months after randomization.
6. Comparison of the difference in left ventricular ejection fraction (LVEF%) measured by echocardiography between the two groups at 24 months after randomization compared to baseline.
7. Comparison of the difference in left ventricular end-systolic diameter (LVIDs) measured by echocardiography between the two groups at 24 months after randomization compared to baseline.
8. Comparison of the difference in left ventricular end-diastolic diameter (LVIDd) measured by echocardiography between the two groups at 24 months after randomization compared to baseline.
9. Comparison of New York Heart Association (NYHA) functional classification between the two groups at 24 months after randomization.
10. Comparison of Kansas City Cardiomyopathy Questionnaire (KCCQ) scores between the two groups at 24 months after randomization.
11. Incidence of adverse events related to fexofenadine.

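### Section 3.7 counts all-cause death in the primary endpoint, but the Section 3.12 row that assigns the primary log-rank test names only cardiac death and leaves its list open

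*Protocol*

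**What the plan says.** Section 3.7 of the protocol defines the primary endpoint as MACCE within 24 months of randomization, "including all-cause death, recurrent myocardial infarction, stroke, hospitalization for heart failure, outpatient or emergency visits due to worsening heart failure". Angina-driven revascularization completes the list. That makes six components, and the list has no open ending.

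The Section 3.12 table has a primary-endpoint row with the same 24-month window. It assigns survival analysis, a Kaplan-Meier curve and the log-rank test. Its description of the endpoint is "MACE, including cardiac death, non-fatal MI, non-fatal stroke, readmission for heart failure, etc".

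The next row of that table, like Section 3.8, has "All-cause death at 24 and 60 months after randomization" as a secondary endpoint. Cardiac death occurs nowhere else in the protocol and is not defined. The schedule in Section 3.11.6 collects MACE events without a component list. Section 4 bases the sample size on this statement: "Assuming an event rate of 16.5% in the control group and 13.2% in the experimental group". It does not say which composite or time horizon those rates describe.

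**The concern.** The trial has one primary test, and the protocol describes the events entering it in two ways that do not agree. The label differs (MACCE or MACE), the death component differs (all-cause or cardiac), and one list is complete while the other ends in *etc.*

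This is not detail left for a statistical analysis plan. The protocol states the item twice and inconsistently, so an analysis plan written from it would inherit both versions. Two things are at stake:

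- **Meaning of the result.** A patient who dies of a non-cardiac cause has an event in one version and may be censored in the other.
- **Error control.** If the definition is still open once the data are unblinded, there are two candidate primary p-values, and the 0.025 level holds only for a version fixed in advance.

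**Working it through.** **1. The two definitions side by side**

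| Event | Section 3.7 | Section 3.12, primary row |
|---|---|---|
| Cardiac death | counted (all-cause death) | named |
| Non-cardiac death | counted (all-cause death) | not named |
| Fatal stroke | counted, as a death and as a stroke | not named: read literally, neither a cardiac death nor a non-fatal stroke |
| Non-fatal MI | counted | named |
| Non-fatal stroke | counted | named |
| Heart-failure hospitalization | counted | named, as readmission |
| Outpatient/emergency heart-failure visit | counted | undetermined (*etc.*) |
| Angina-driven revascularization | counted | undetermined (*etc.*) |

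One component conflicts (death) and two of the six are undetermined. The open ending could take in the last two rows. It does not naturally widen a named item from cardiac death to all-cause death, particularly in a table whose next row uses the all-cause term.

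**2. Can the sample size show which version was meant?**

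Inputs from Section 4: 16.5% against 13.2%, one-sided 0.025, 80% power, 2-year enrollment, 10% dropout, 1402 per group.

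- Hazard ratio under exponential survival: ln(1 − 0.132) / ln(1 − 0.165) = 0.785.
- Events by Schoenfeld's formula: 4(1.96 + 0.842)² / (ln 0.785)², giving 537.
- Rates taken as 24-month rates, uniform 2-year accrual and everyone followed to year 4: mean event probability 0.2133, so 537 / 0.2133 / 2 = 1259 per group. Dividing by 0.9 gives 1399, close to the stated 1402.
- Fixed 24-month follow-up: mean event probability 0.1485, so 537 / 0.1485 / 2 = 1808 per group. Dividing by 0.9 gives 2009, which does not match.

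The stated number can be approximated, but nothing in it depends on how death is defined. It cannot settle the question.

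**3. Does the choice affect power, and in which direction?**

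Starting point: 1402 × 0.9 ≈ 1262 evaluable per group and fixed 24 months. Expected events are 1262 × (0.165 + 0.132) = 375. Power is Φ(½√375 × |ln 0.785| − 1.96) = 64.9%.

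Assume, since the protocol gives no split, that non-cardiac deaths are 5-20% of control-group first events and are dropped:

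- **Relative effect unchanged.** Rates become 15.675%/12.54% (5%) to 13.2%/10.56% (20%). Events fall to 356-300 and power to 62.3%-53.9%.
- **Non-cardiac deaths equally frequent in both groups.** Rates become 15.675%/12.375% to 13.2%/9.9%. Events fall to 354-292, but power rises to 67.0%-74.3%.

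The event count changes either way. The direction of the power effect depends on component-level effects that the protocol does not give.

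**4. Type I error if the better version were reported**

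Treat the narrower composite as nested in the wider one, with f the shared fraction of events (assumed). Under no effect the two log-rank statistics have correlation ρ ≈ √f. The error of the better of two one-sided 0.025 tests is 1 − Φ₂(1.96, 1.96; ρ).

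| f | ρ | error |
|---|---|---|
| 0.95 | 0.975 | 0.0302 |
| 0.90 | 0.949 | 0.0324 |
| 0.80 | 0.894 | 0.0354 |
| 0.60 | 0.775 | 0.0398 |

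The first two rows represent a difference in non-cardiac deaths only. The last two represent the undetermined components also being read as excluded. Simulated log-rank tests (2804 patients, 16.5% at 24 months assumed in both groups, 6000 runs per f) gave correlations of 0.976, 0.951, 0.895 and 0.770, and better-of-two errors of 0.029-0.037 with a Monte Carlo standard error of about 0.002.

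**The case against.** The best defence is that the 3.12 row is shorthand. Section 3.7 is the dedicated endpoint section and gives the full list. The 3.12 table is loose elsewhere too: it scales ventricular diameters to body surface area and adds a 12-month point for NYHA class and KCCQ, neither of which is in Section 3.8. A list that begins with *including* and ends in *etc.* does not strictly exclude non-cardiac death, and 3.7 itself also uses *including*. All this makes it likely that 3.7 is the intended definition. It does not make the two texts agree, and the protocol never says that 3.7 prevails. The point therefore stands as *not a named event*, not as an express exclusion.

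The error figures are also open to challenge. They describe selective reporting, which nothing in the protocol proposes. Section 3.11.3 keeps statistical analysis blinded, and an analysis plan not at hand may fix the composite in time. The shared fractions are assumed, nesting is assumed although *etc.* could add events outside 3.7, and ρ = √f ignores patients whose first event falls at different times in the two composites. These objections are fair. The figures are illustrative and the finding does not rest on them.

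Finally, event capture is not shown to be at risk: the Section 3.11.6 schedule makes post-enrollment medical events mandatory at every follow-up. That limits the problem to definition and analysis.

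**Conclusion.** The concern holds. The one primary test has two inconsistent event definitions, and the protocol does not rank them. The textual finding needs no assumption: death conflicts, and two of the six 3.7 components are undetermined in 3.12.

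The consequence for type I error is conditional. If the choice were made after unblinding and the better version reported, the one-sided level would be about 0.030-0.032 at 95-90% shared events and about 0.035-0.040 at 80-60%, given nested composites and assumed fractions. No direction can be claimed for power.

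Because it concerns the event definition of the sole primary analysis, it must be corrected before unblinding.

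**What to change.** Before unblinding, replace the description in the 3.12 primary row with the six components of 3.7: all-cause death, recurrent MI, stroke, heart-failure hospitalization, outpatient/emergency visit for worsening heart failure, and angina-driven repeat revascularization. Delete cardiac death and *etc.* State that the log-rank test and Kaplan-Meier curve use time to the first of these within 24 months of randomization. If a narrower MACE is also wanted, list it as a named secondary endpoint with its own closed list and a definition of cardiac death.

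Useful alongside, though not essential to this point:

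- Rename the schedule row in 3.11.6 to MACCE, and confirm that the event form records each component.
- State in Section 4 which composite and horizon the 16.5% and 13.2% describe.

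The cost is wording in a protocol amendment. Secondary endpoints 1-5 in Section 3.8 already cover every 3.7 component, so no new outcome is introduced. For this point, the sample size needs re-checking only if the Section 4 rates turn out to belong to another composite or horizon.

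### The only test named for 24-month MACCE is an unadjusted log-rank: valid, but it leaves unused an efficiency gain from baseline factors the protocol already makes mandatory

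*Protocol*

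**What the plan says.** The Primary Endpoint row of the table in Protocol section 3.12 gives the method as "Survival analysis, Kaplan-Meier survival curve, Log-rank test", analysed at month 24. No adjusted or stratified test is named, and section 3.11.2 states no stratification factors for the randomization. As written, neither design nor analysis uses prognostic information.

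That information is collected. Section 3.11.5 requires the site to "Complete a detailed medical history record, including age, gender, NYHA functional status, risk factors (hypertension, smoking, diabetes, etc.), and previous cardiovascular diseases". The schedule in section 3.11.6 marks history, laboratory tests including renal function, and echocardiography with LVEF as mandatory at baseline.

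Section 4 sizes the trial "with a one-sided α value set at 0.025 and a power (1- β) of 0.8", "Assuming an event rate of 16.5% in the control group and 13.2% in the experimental group". It concludes: "Considering a 10% dropout rate, 1402 patients will need to be enrolled in each group, totaling 2804 patients".

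**The concern.** In a post-STEMI population, patients probably differ in their risk of MACCE for reasons visible at baseline. A test that ignores those differences treats explainable variation as noise. If the covariates predict the outcome, a test that uses them has a better chance of detecting the same treatment effect, with no extra patients or events. The primary test decides the trial, and covariates can be chosen credibly only before unblinding. Leaving this to the statistical analysis plan does not settle it, because the protocol itself names the test.

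**Working it through.** **Inputs from the protocol.** Event rates 16.5% and 13.2%, one-sided alpha 0.025, power 0.80, 1:1 allocation, 10% dropout, 2-year accrual, 1402 per group (section 4); endpoint counted to 24 months (section 3.7). **Assumed, because the protocol gives no figure:** the prognostic strength of the baseline factors.

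**1. Planned events.** Reading the rates as 24-month risks, HR = ln(0.868)/ln(0.835) = 0.785, so |ln HR| = 0.242. Schoenfeld: 4 × (1.960 + 0.842)² / 0.242² gives 537 events. Freedman's formula gives 542.

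**2. The stated sample size.** It reproduces with exponential survival, 2 years of uniform accrual and a common close 2 years after the last patient. Event probabilities are then 23.6% and 19.1%, average about 21.3%. Schoenfeld: 537/0.2133 = 2518, and 2518/0.9 = 2797. Freedman: 2541/0.9 = 2823. The stated total is 2804.

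**3. Power at 24 months.** If each patient counts only to month 24, the average event probability is (16.5% + 13.2%)/2 = 14.85%. Power is Φ(√D × 0.242/2 − 1.960).
- No dropout: D = 2804 × 0.1485 = 416; power 69%.
- 10% removed: D = 2524 × 0.1485 = 375; power 65%.

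This is the base for the gains below. Its distance from 80% comes from the follow-up assumption, not from the choice of test.

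**4. Gain by formula.** If covariates explain a share R² of the variance of the log-rank score, the expected test statistic is divided by √(1 − R²). From 64.9% power the statistic is 0.383 + 1.960 = 2.342. With R² = 0.10 it becomes 2.342/√0.90 = 2.469, and power is Φ(2.469 − 1.960) = 69.5%, a gain of 4.6 points. The same step gives +0.9 at R² 0.02, +2.2 at 0.05, +3.4 at 0.075 and +7.0 at 0.15.

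**5. Gain by simulation.** 1,402 per arm; marginal 24-month risks held at 16.5% and 13.2%; 10% dropout; one normal risk score acting on the log hazard; 1,500 to 3,000 trials per setting. The C 0.62 row for Cox also draws on runs with 2524 evaluable patients. Unadjusted power at C 0.66, 0.71 and 0.75 was 67%, 67% and 69%.

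| Assumed C | SD of log-hazard score | Gain, adjusted log-rank (points) | Gain, adjusted Cox (points) |
|---|---|---|---|
| about 0.62 or below | 0.4 or below | 0-1 | 0-1 |
| 0.66 | 0.6 | 3 | 3 |
| 0.71 | 0.8 | 3-4 | 5-6 |
| 0.75 | 1.0 | 5-6 | 8-9 |

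Under the 2-4 year follow-up that reproduces the stated total, the Cox gain is similar or larger (+1.8 at C 0.62, +2.8 at 0.67, +6.1 at 0.70, +9.9 at 0.75). The direction therefore does not depend on how the follow-up is read.

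**The case against.** The strongest reply is that nothing here is an error. The unadjusted log-rank is valid, controls type I error and suits a sample size built on marginal event rates. That stands: this is an efficiency point only.

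A reader might go further and infer that the plain test throws away 3-8 points of power because strong prognostic factors are ignored. The documents do not support that, for three reasons.
- The protocol nowhere shows that the factors are strong. The endpoint mixes death, infarction, stroke, heart failure and angina-driven revascularization, and one short covariate list may predict that mixture poorly. With weak factors the gain is close to nil.
- Against the protocol's marginal effect the plain test loses nothing as patients become more heterogeneous: its power stayed at 67-69% across the settings. What is at issue is a gain not taken up.
- The upper end of such a range belongs to the Cox test, which estimates a conditional hazard ratio. The adjusted log-rank, which keeps the marginal comparison, gains less.

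Nor should the gap between about 65-69% and 80% power be blamed on the log-rank (working, steps 2 and 3).

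The simulation is also idealised: one correctly specified covariate, never missing. Several real covariates of unknown functional form may do less well. Timing matters too. Section 3.11.6 ties baseline to before discharge, while section 3.11.4 starts treatment immediately after randomization, so some baseline values could follow the first dose. The echocardiographic inclusion criterion asks only for wall-motion abnormality; LVEF comes from the schedule. These points limit the size of the gain and shape the fix, but do not remove the case for adjustment.

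**Conclusion.** The point holds as a modest, inexpensive efficiency improvement to a method the protocol fixes. With a covariate-adjusted log-rank the expected gain runs from about 0-1 point to about 5-6 points of power over an assumed C-index from about 0.62 or below up to 0.75. It rests on that assumed C, on marginal 24-month risks of 16.5% and 13.2%, and on covariates that are measured before randomization and reasonably modelled. It would not by itself restore 80% power at 24 months; the sample-size question needs its own answer.

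**What to change.** In the Primary Endpoint row of section 3.12, name one primary test: a covariate-adjusted log-rank test. Fix a short covariate list before unblinding: age, diabetes, previous MI, LVEF and eGFR. Use only values measured before randomization, and state a simple rule for missing baseline values. Keep the Kaplan-Meier curves and report the unadjusted log-rank as a sensitivity analysis. Carry the same wording into the statistical analysis plan.

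The cost is one table row, slightly more analysis work and a covariate list that must be locked in advance. No new patients or procedures are needed.
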